## 9.2 Sample size determination

The study is sized to characterize the PFS benefit of durvalumab in combination with olaparib versus durvalumab monotherapy in first-line patients with unresectable Stage IV UC.

Approximately 150 patients globally will be randomized in a 1:1 ratio to either the durvalumab + olaparib treatment group or the durvalumab + placebo treatment group, 75 patients per arm. The randomization will be stratified based on HRR status (mutant versus wild type) and Bajorin risk index (0 versus 1 versus 2).

The DCO for the primary analysis of PFS will occur when approximately 118 PFS events have occurred across both treatment groups (79% maturity). Assuming a median survival of 3 months for durvalumab monotherapy and recruitment of 150 patients in 6 months, it is estimated that this DCO will occur 7 months following recruitment of the last patient.

If the true PFS hazard ratio (HR) is 0.55 (likely to correspond to an 82% prolongation of PFS), the study will have 90% power to demonstrate a statistically significant difference for PFS at the 2-sided 5% significance level.

The smallest treatment difference that could be statistically significant at the primary analysis of PFS is an HR of 0.69 (assuming a 2-sided p-value of 0.5).

There will be up to 2 analysis timepoints for OS. The first OS analysis will occur at the same time as the primary PFS analysis and will be based on an estimated 44 OS events across therapies (29% maturity), and the second OS analysis will occur when

approximately 100 OS events have occurred (67% maturity). With an approximate 6-month recruitment period and an assumed median OS of 16 months in the durvalumab + placebo arm, it is anticipated that the final analysis will be performed at approximately 27 months after the last patient has been recruited.

Assuming the true OS HR is 0.75, the study will have 30% power to demonstrate a statistically significant OS effect with a 5% 2-sided significance level, allowing for 2 analyses of the data. The smallest treatment difference at the second analysis of OS that could be statistically significant is an HR of 0.68.

### 9.3 Populations for analyses

Definitions of the analysis sets for each outcome variable are provided in [Table 15](#).

**Table 15 Summary of outcome variables and analysis populations**

Outcome variable	Populations
Efficacy data	
PFS	Full analysis set (all patients for the primary analysis and the subset of patients with HRRm for the secondary analysis)
ORR, DoR, PFS6, OS, OS18, PROs	Full analysis set (all patients; ORR, DoR and PFS6 will be repeated in the subset of patients with HRRm) DoR will be based on the subset of patients in the analysis population who achieved objective tumor response
Demography	Full analysis set
PK data	PK analysis set
Safety data	
Exposure	Safety analysis set
AEs	Safety analysis set
Laboratory measurements	Safety analysis set
WHO/ECOG performance status	Safety analysis set

**Table 15 Summary of outcome variables and analysis populations**

Outcome variable	Populations
Vital signs	Safety analysis set

AE Adverse event; DoR Duration of response; ECOG Eastern Cooperative Oncology Group; ORR Overall response rate; OS Overall survival; OS18 patients alive at 18 months; PFS Progression-free survival; PFS6 Progression-free at 6 months; PK Pharmacokinetics; PRO Patient-reported outcome; WHO World Health Organization.

### **9.3.1 Full analysis set**

The FAS will include all randomized patients. Treatment arms will be compared based on randomized study treatment regardless of the study treatment received. Patients who were randomized but did not subsequently go on to receive study treatment will be included in the analysis in the treatment arm to which they were randomized.

The FAS will be used for the primary efficacy analysis of PFS and all secondary efficacy analyses (including PROs).

### **9.3.2 Safety analysis set**

The safety analysis set will consist of all patients who received at least 1 dose of study treatment. Safety data will not be formally tested but will be summarized using the safety analysis set per the treatment received, that is, erroneously treated patients (eg, patients randomized to durvalumab + placebo who receive 1 or more doses of olaparib in error, will be reported in the durvalumab + olaparib group) will be summarized per the treatment they received.

### **9.3.3 PK analysis set**

All patients who receive at least 1 dose of study treatment per the protocol for whom any post-dose data are available and who do not violate or deviate from the protocol in ways that would significantly affect the PK analyses will be included in the PK analysis set. The population will be defined by the Study Physician, Pharmacokineticist, and Statistician prior to any analyses being performed.

## 9.4 Statistical analyses

Analyses will be performed by AstraZeneca or its representatives. A comprehensive SAP will be developed and finalized before database lock and will describe the patient populations to be included in the analyses, and procedures for accounting for missing, unused, and spurious data. This section is a summary of the planned statistical analyses of the primary, secondary, and exploratory endpoints. Any deviations from this plan will be reported in the CSR.

Descriptive statistics will be used for all variables, as appropriate, and will be presented by treatment group. Continuous variables will be summarized by the number of observations, mean, standard deviation, median, minimum, and maximum. Categorical variables will be summarized by frequency counts and percentages for each category. Unless otherwise stated, percentages will be calculated out of the population total for the corresponding treatment arm.

Baseline will be the last assessment of the variable under consideration prior to the intake of the first dose of IP, except for efficacy variables. For efficacy variables, baseline is defined as the last visit prior to randomization.

Efficacy and PRO data will be summarized and analyzed based on the FAS. PK data will be summarized and analyzed based on the PK analysis set. Safety data will be summarized on the safety analysis set.

All outputs will be summarized by treatment arm.

Results of all statistical analyses will be presented using a 95% CI and a 2-sided p-value, unless otherwise stated.

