**Table 1 Schedule of assessments for patients who are receiving study treatment**

	Screening	C1 a	C2 a	C3 a	C4 a	C5 to PD a,b	EOT visit c	For details, see Section	
Week	-4 to -1	0	q4w ±3 days unless dosing needs to be held for toxicity reasons						
Day	-28 to -1	1	q28days ±3 days unless dosing needs to be held for toxicity reasons						
Pharmacokinetics									
Durvalumab PK sample (serum)		X n	X o		X o			8.5.1.1	
Olaparib PK sample (plasma)		X o	X o		X o			8.5.1.2	
Monitoring									
WHO/ECOG performance status	X	X	X	X	X	X	X	8.2.5	
AE/SAE assessment p	<----->								8.3
Drug accountability		X	All visits						6.3
IP administration									
Durvalumab q		X r	X r	X r	X r	X r		6.1.1.1	
Olaparib/placebo q		X	X	X	X	X		6.1.1.2	
Other assessments and assays									
Tumor biopsy (FFPE sample) s	X s					X s		8.1.2, 8.8.1.1	
Genetic sample	X							8.7, Appendix D	
Durvalumab immunogenicity assessment (ADA sampling to identify ADA responses in patient circulation)		X o	X o		X o			8.5.2	
Whole blood for gene expression (PaxGene-RNA tubes)	X o	X o	X o			X o		8.8.1.2	
Whole blood – exploratory analysis (mandatory) t	X	X	X	X	X	X	X	8.8.1.3	
Urine (mutational analysis)	X	X	X	X	X	X	X	8.8.1.4	
ctDNA (plasma)	X	X	X	X	X	X	X	8.8.1.5	
EORTC QLQ-C30 and EQ-5D-5L u		X	q4w (±7 days relative to Cycle 1 Dose 1 date) until treatment discontinuation						8.1.4.1, 8.1.4.2

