#### **EORTC QLQ-C30**

The EORTC QLQ-C30 consists of 30 questions that can be combined to produce 5 function scales (physical, role, cognitive, emotional, and social), 3 symptom scales (fatigue, pain, and nausea/vomiting), and a global measure of health status. The EORTC QLQ-C30 will be scored according to the EORTC QLQ-C30 scoring manual ([Fayers et al 2001](#)). An outcome variable consisting of a

score from 0 to 100 will be derived for each of the symptom scales, each of the function scales, and the global health status scale in the EORTC QLQ-C30 according to the EORTC QLQ-C30 scoring manual. Higher scores on the global health status and function scales indicate better health status/function, but higher scores on symptom scales represent greater symptom severity.

Definition of clinically meaningful changes

Changes in score compared with baseline will be evaluated. A minimum clinically meaningful change is defined as an absolute change of  $\geq 10$  in the score from baseline for scales from the EORTC QLQ-C30 (Osoba et al 1998). For example, a clinically meaningful improvement in physical function (as assessed by EORTC QLQ-C30) is defined as an increase of  $\geq 10$  in the score from baseline, whereas a clinically meaningful deterioration is defined as a decrease of  $\geq 10$  in the score from baseline. At each post-baseline assessment, the change in symptoms/ functioning from baseline will be categorized as improvement, no change, or deterioration as shown in Table 16. A patient’s best overall response in symptoms, function, or global health status/QoL will be derived as the best response the patient achieved, based on evaluable PRO data collected during the study period. Additional details will be provided in the SAP.

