**Table 16 Mean change and visit response in health-related quality of life**

Score	Change from baseline	Visit response
EORTC QLQ-C30 global quality of life score	$\geq +10$ $\geq -10$ Otherwise	Improvement Deterioration No change
EORTC QLQ-C30 symptom scales	$\geq +10$ $\geq -10$ Otherwise	Deterioration Improvement No change
EORTC QLQ-C30 function scales	$\geq +10$ $\geq -10$ Otherwise	Improvement Deterioration No change

EORTC QLQ-C30 European Organisation for Research and Treatment of Cancer 30-item core quality of life questionnaire.

For each subscale, if  $< 50\%$  of the subscale items are missing, then the subscale score will be divided by the number of non-missing items and multiplied by the total number of items on the subscales (Fayers et al 2001). If at least 50% of the items are missing, then

that subscale will be treated as missing. Missing single items are treated as missing. The reason for any missing questionnaire will be identified and recorded. If there is evidence that the missing data are systematic, missing values will be handled to ensure that any possible bias is minimized.

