#### Time to symptom deterioration

For each of the symptoms scales in the EORTC QLQ-C30, time to symptom deterioration will be defined as the time from randomization until the date of the first clinically meaningful symptom deterioration (an increase of  $\geq 10$  in the score from baseline) or death (by any cause) in the absence of a clinically meaningful symptom deterioration, regardless of whether the patient discontinues study treatment or receives another anticancer therapy prior to symptom deterioration. Death will be included as an event only if the death occurs within 2 visits of the last PRO assessment where the symptom change could be evaluated.

Patients whose symptoms (as measured by EORTC QLQ-C30) have not shown a clinically meaningful deterioration and who are alive at the time of the analysis will be censored at the time of their last PRO assessment where the symptom could be evaluated. Also, if symptoms deteriorate after 2 or more missed PRO assessment visits or the patient dies after 2 or more missed PRO assessment visits, the patient will be censored at the time of the last PRO assessment where the symptom could be evaluated. If a patient has no evaluable visits or does not have baseline data they will be censored at Day 0. The population for the analysis of time to symptom deterioration will include a subset of the FAS who have baseline scores of  $\leq 90$ .

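### Table 16 prints its second cut-off as at least −10 instead of at most −10, so unchanged QLQ-C30 scores count as changed and large falls count as no change

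*Protocol*

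**What the plan says.** **Categories of change.** Section 9.4.1.3 (EORTC QLQ-C30) sets the minimum meaningful change at 10 points in absolute value. It gives physical function as its example: "a clinically meaningful deterioration is defined as a decrease of" at least 10 points. The same paragraph names Table 16 as the rule for sorting each post-baseline change into improvement, no change or deterioration.

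Table 16 gives three cut-offs, identical for the global quality of life, symptom and function rows: "\geq +10$ $\geq -10$ Otherwise", that is, at least +10, at least −10, and everything else. For global and function scores the labels in that order are Improvement, Deterioration, No change. For symptom scales they are Deterioration, Improvement, No change.

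**Baseline.** Section 9.4 has a general rule, "Baseline will be the last assessment of the variable under consideration prior to the intake of the first dose of IP", and an exception: "For efficacy variables, baseline is defined as the last visit prior to randomization". Section 9.3.1 uses the full analysis set for "all secondary efficacy analyses (including PROs"), and Table 15 places "ORR, DoR, PFS6, OS, OS18, PROs" under its efficacy heading. In Table 1 the QLQ-C30 and EQ-5D-5L are first marked at Cycle 1 and then "q4w (±7 days relative to Cycle 1 Dose 1 date) until treatment discontinuation"; the Screening column, where randomization is marked, has no PRO entry. For time to deterioration: "If a patient has no evaluable visits or does not have baseline data they will be censored at Day 0".

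**The concern.** Because the text points to Table 16 as the categorization rule, a programmer would reasonably code from the table. As printed, the table gives a patient with no change a change label and gives a patient with a large fall the label No change. It also puts a change of +10 or more in two categories at once.

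The global health status/QoL, physical function, fatigue and pain scales named in the secondary PRO objective are all affected. Best overall response is built on these labels, so the ordering is disturbed as well. On function scales a fall of 25 (No change) would rank above a change of 0 (Deterioration). On symptom scales one visit with an unchanged score would make the patient's best response Improvement.

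The baseline wording matters for a separate reason. If PROs count as efficacy variables, the exception in Section 9.4 asks for a value that the schedule does not collect.

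**Working it through.** There is no planned figure to reproduce, because the point concerns definitions. The check applies both rules to the same changes and compares the labels.

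**1. The rules side by side, function and global scores, Table 16 read from the top**

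| Change c | Table 16 as printed | Text of Section 9.4.1.3 |
|---|---|---|
| c ≥ +10 | Improvement (also satisfies the second line) | Improvement |
| −10 < c < +10 | Deterioration | No change |
| c < −10 | No change | Deterioration |

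Symptom scales mirror this: between −10 and +10 the table gives Improvement, and below −10 it gives No change where the text implies improvement. Apart from a change of exactly −10, every change below +10 gets the wrong label.

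**2. Attainable changes.** Section 8.1.4.1 gives 7-point responses for the 2 global items and 4-point responses for the others. Items per scale are taken as 2 (global), 5 (physical), 3 (fatigue) and 2 (pain). Scores on 0–100 then move in steps of 100/(items × item range), and n steps give 2n + 1 possible changes.

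- Global: 12 steps of 8.33, 25 changes. Wrong: 3 small changes (−8.33, 0, +8.33) + 11 larger falls = 14 of 25.
- Physical: 15 steps of 6.67, 31 changes. Wrong: 3 + 14 = 17 of 31.
- Fatigue: 9 steps of 11.11, 19 changes. Wrong: 1 + 9 = 10 of 19.
- Pain: 6 steps of 16.67, 13 changes. Wrong: 1 + 6 = 7 of 13.

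These count possible values, not patients. A change of exactly −10 cannot occur on any of the four scales.

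**3. Illustrative share of visits.** The protocol gives no SD for change. Assume X ~ Normal(0, SD). Share wrong = P(−10 ≤ X < 10) + P(X < −10).

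- SD 15: 0.495 + 0.252 = 0.747, about 75%
- SD 20: 0.383 + 0.309 = 0.692, about 69%
- SD 25: 0.311 + 0.345 = 0.656, about 66%

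**4. Where the labels are used.** Visit response uses Table 16 directly, and best overall response is built on it. Section 9.4.2.7 also compares best symptom and HRQoL/function response rates by logistic regression. It does not say whether those rates come from Table 16 or from the separately defined improvement rates, so that reach is only possible. Time to deterioration and the improvement rates carry their own 10-point definitions with the correct direction. The mixed model uses no cut-off.

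**5. Baseline.** Section 9.3.1 and Table 15 put PROs with efficacy. Section 9 lists the secondary efficacy variables without PROs. Sections 9.4.1.1 and 9.4.1.3 derive efficacy and PRO variables separately, and Section 9.4 itself names efficacy data and PRO data as two things. Under the general rule the Cycle 1 questionnaire serves as baseline, since the note to Table 1 places treatment-day assessments before infusion unless otherwise indicated. Under the exception, no patient has a scheduled PRO baseline.

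**The case against.** The strongest defence is that the intended rule is plain. The text gives the 10-point rule in words, and the table as printed is incoherent because its first two lines overlap, so a careful analyst would notice. The PRO analyses listed in Table 17 do not depend on Table 16, PROs carry no alpha under Sections 9.1 and 9.4.10, and more detail on best response is promised for the SAP. All of this stands, and it limits the consequences. It does not remove the contradiction, since the text itself hands categorization to the table. A sign lost in reading the PDF cannot be fully excluded, but the same sign appears in all three rows.

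Two stronger readings are tempting, and the documents support neither:

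- A reader might infer that the baseline rule leaves every patient without a PRO baseline, so that change from baseline cannot be analysed and everyone is censored at Day 0. That follows only if PROs are efficacy variables for the purpose of Section 9.4. Section 9.3.1 and Table 15 assign analysis populations and do not define baseline, while the sections that define variables keep PROs apart. The protocol also calls the VES-13 a baseline measure although Table 1 schedules it at Cycle 1. What remains is an ambiguity.
- A reader might infer that the Table 16 error spoils the whole QLQ-C30 objective. It does not, because the time-to-event and improvement-rate definitions are correct where they stand.

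**Conclusion.** Table 16 is wrong as printed and contradicts the text that invokes it. On all four scales of the secondary PRO objective, more than half of the attainable changes would be mislabelled. As an illustration, about 66% to 75% of visit labels would be wrong if changes are Normal with mean 0 and SD 15 to 25. Both the distribution and the SDs are assumed, and the figure applies only if the table is programmed literally.

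The effect is confined to visit response, best overall response and possibly the best-response regressions in Section 9.4.2.7. The primary PFS analysis and the OS analysis are untouched.

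The baseline point is secondary: the protocol does not settle which of its two baseline rules governs PROs, and only one of them fits the schedule.

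**What to change.** In Table 16, change the second cut-off from ≥ −10 to ≤ −10 in all three rows. Table and text then agree for every attainable change: 0 becomes No change on every scale, and a fall of 10 or more becomes Deterioration (function and global) or Improvement (symptoms).

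In Section 9.4, add: *For PRO variables, baseline is the last assessment before the first dose of IP.* The Cycle 1 pre-dose questionnaire supplies it.

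The cost is three table cells and one sentence. No visit, assessment, treatment or sample size changes. Any later specification that carries Table 16 over should be checked for the same sign.

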### 9.4.1 Outcome measures for analysis

#### 9.4.1.1 Calculation or derivation of efficacy variables

The analysis of the primary endpoint, PFS, and the analyses of the secondary endpoints, ORR, DoR, and PFS6, will be based on the site Investigator assessments per RECIST 1.1. Secondary endpoints OS and OS18 will be evaluated from all-cause mortality.

BICR may be performed at AstraZeneca's discretion.

### **RECIST 1.1-based endpoints**

All RECIST 1.1 assessments, whether scheduled or unscheduled, will be included in the calculations. This is also regardless of whether a patient discontinues study treatment or receives another anticancer therapy.

At each visit, patients will be assigned a RECIST 1.1 visit response of CR, PR, SD, or PD depending on the Investigator-reported status of their disease compared with baseline and previous assessments. Baseline will be assessed within the 28 days prior to randomization. If a patient has had a tumor assessment that cannot be evaluated, then the patient will be assigned a visit response of NE; unless there is evidence of progression, in which case the response will be assigned as PD.

Please refer to [Appendix F](#) for the definitions of CR, PR, NE, SD, and PD.

### **Progression-free survival**

PFS (per RECIST 1.1 as assessed by the site Investigator) will be defined as the time from the date of randomization until the date of objective disease progression or death (by any cause in the absence of progression) regardless of whether the patient withdraws from therapy or receives another anticancer therapy prior to progression (ie, date of event or censoring – date of randomization + 1). Patients who have not progressed or died at the time of analysis will be censored at the time of the latest date of assessment from their last evaluable RECIST 1.1 assessment. However, if the patient progresses or dies after 2 or more consecutive missed visits, the patient will be censored at the time of the latest evaluable RECIST 1.1 assessment prior to the 2 missed visits. If the patient has no evaluable visits or does not have baseline data, they will be censored at Day 1 unless they die within 2 visits of baseline; then they will be treated as an event with date of death as the event date.

The PFS time will always be derived based on scan/assessment dates and not visit dates.

RECIST 1.1 assessments/scans contributing toward a particular visit may be performed on different dates. The following rules will be applied:

- For Investigator assessments, the date of progression will be determined based on the earliest of the RECIST 1.1 assessment/scan dates of the component that indicates progression.

- When censoring a patient for PFS, the patient will be censored at the latest of the scan dates contributing to a particular overall visit assessment.

### **Overall survival**

OS is defined as the time from the date of randomization until death due to any cause. Any patient not known to have died at the time of analysis will be censored based on the last recorded date on which the patient was known to be alive.

Note: Survival calls will be made following the date of DCO for the analysis. If patients are confirmed to be alive or if the death date is after the DCO date, these patients will be censored at the date of DCO. Death dates may be found by checking publicly available death registries.

### **Objective response rate**

ORR (per RECIST 1.1 using Investigator assessments) is defined as the number (%) of patients with at least 1 visit response of CR or PR. Data obtained up until progression, or the last evaluable assessment in the absence of progression, will be included in the assessment of ORR. Patients who go off treatment without progression, receive a subsequent therapy, and then respond will not be included as responders in the ORR.

